8.2.2.3. Biomarkers

Kidney Function Biomarkers

Kidney function biomarkers are assessed by: sodium and fractional excretion of sodium at Baseline and Day 1 to Day 7; urine creatinine, urinary BUN/urea, urea clearance, fractional excretion of urea and urine output at Baseline and Day 1 to Day 28; and serum creatinine, BUN, and proteinuria at Baseline and Day 1 to Day 90.

The observed values and change from baseline for kidney function markers will be calculated by visit and summarized with descriptive statistics.

All kidney function markers will be listed.

Urinary Biomarkers for Proximal Tubular Cell Damage

Proximal tubular damage is assessed by the following urinary biomarkers: KIM-1, IL-18 and GST-alpha (urinary concentration and normalized for urinary creatinine concentration) at Baseline and each scheduled visit up to Day 28.

The observed values and change from baseline for urinary biomarkers will be calculated by visit and summarized with descriptive statistics.

Time-course plots similar to the plot being produced for the primary endpoint will be presented for mean KIM-1, IL-18 and GST-alpha, displaying the optimal recAP and placebo groups only.

As described in Section 8.1.5, two different kits were used for GST-alpha testing and therefore data will be summarized separately depending on which kit was used to test.

All urinary biomarkers will be listed.

Biomarkers for Systemic Inflammation

Biomarkers for systemic inflammation are assessed by IL-6, CRP and LBP at Baseline and each scheduled visit up to Day 28.

The observed values and change from baseline for biomarkers for systemic inflammation will be calculated by visit and summarized with descriptive statistics.

Time-course plots similar to the plot being produced for the primary endpoint will be presented for mean IL-6, CRP and LBP, displaying the optimal recAP and placebo groups only.

All biomarkers for systemic inflammation will be listed.

8.3. Other Efficacy Endpoints

Composite Endpoints

Patients that meet, or do not meet at least 1 of the following criteria will be summarized by counts and percentages for each composite endpoint:

Composite Endpoint 1:

1. Received RRT (prior to Day 28 [inclusive]) or
2. Died (prior to Day 28 [inclusive])

Composite Endpoint 2:

1. eGFR < 60 mL/min (at Day 60, estimated by the CKD-EPI formula based on serum creatinine) or
2. Dialysis dependency (up to Day 60) or
3. Died (prior to Day 60)

Composite Endpoint 3:

1. eGFR < 60 mL/min (at Day 90, estimated by the CKD-EPI formula based on serum creatinine) or
2. Dialysis dependency (up to Day 90) or
3. Hospitalized for a new episode of AKI (prior to Day 90) or
4. Died (prior to Day 90)

Exploratory analysis of each composite endpoint will be undertaken for the comparison of the optimal recAP dose and placebo using a logistic regression model with treatment group and site as explanatory variables. The odds ratio and associated 95% confidence interval from the comparisons of the optimal recAP dose versus Placebo will be presented together with the p-value for this comparison.

Serology

Serology is assessed by IgG, IgE, and total immunoglobulin at Baseline, Day 14 and Day 28.

The observed values and change from baseline for IgG, IgE, and total immunoglobulin will be calculated by visit and summarized with descriptive statistics.

All Serology data will be listed.

Anti-Drug Antibody Data

All anti-drug antibody data will be listed.

Quality of Life

Quality of Life is assessed by the EQ-5D questionnaire at Baseline, ICU/Intermediate care discharge, and Day 90.

The questionnaire assesses 5 dimensions: mobility, self-care, usual activities, pain/discomfort and anxiety/depression. Each dimension has 5 response options (no problems, slight problems, moderate problems, severe problems, and extreme problems) that reflect increasing levels of difficulty. The patient will be asked to indicate his/her current health state by selecting the most appropriate level in each of the 5 dimensions.

The questionnaire also includes a visual analogue scale, where the patient will be asked to rate current health status on a scale of 0-100, with 0 being the worst imaginable health state.

The EQ-5D responses from each dimension will be summarized with counts and percentages by treatment group and visit.

The observed values and change from baseline in visual analog scale will be calculated by visit and summarized with descriptive statistics.

All EQ-5D data will be listed.

Discharge from ICU/Intermediate care for Day 1 to Day 28 and Day 1 to Day 90

Total time in ICU/Intermediate care is calculated as the number of days a patient has been in the ICU/Intermediate care from the start of first study drug infusion to discharge where discharge is defined as the time of actual transfer (up to Day 28 and Day 90) and will be summarized by the descriptive statistics. For the calculation of Total time in ICU/Immediate care for Day 1 to 28 if a subject discontinued or died prior to Day 28 whilst still in ICU, the ICU discharge date is assumed as Day 28. For the calculation of Total time in ICU/Immediate care for Day 1 to 90, if a subject discontinued or died whilst still in ICU, then the discharge date will be assumed as taking the maximum of Day 28 or study discontinuation date.

Time to being discharged from ICU/Intermediate care will be compared between treatment groups by displaying Kaplan-Meier plots, where discharge is defined as the time when the decision was made to transfer the patient (as opposed to the time of actual transfer). Time to being discharged from ICU/Intermediate care is calculated as:

Planned discharge date from ICU/Intermediate care – Start date of study drug infusion + 1.

For patients that have been discharged from the ICU/Intermediate care and had to be readmitted, only their first case of admission will be used to calculate time to being discharged from the ICU/Intermediate care. Patients that have transferred to another ICU/Intermediate care will not be classed as discharged from the ICU/Intermediate care. Patients that have not been discharged from the ICU/Intermediate care will be censored at Day 28 (when died or discontinued prior to Day 28) or on the date of study withdrawal (when died or discontinued after Day 28).

A table of the corresponding Kaplan-Meier estimates will be presented displaying the number of patients at risk, number of patients censored, number of patients discharged from ICU/Intermediate care, cumulative number of patients discharged from ICU/Intermediate care, Kaplan-Meier estimate, and standard errors of the Kaplan-Meier

estimates. Summary statistics (based on the Kaplan-Meier analysis) for the time to discharge from ICU/Intermediate care will also be included in a separate table.

Exploratory analysis of time to being discharged from the ICU/Intermediate care will be undertaken for the comparison of the optimal recAP dose and placebo using a log rank test stratified by site. The hazard ratio, associated 95% confidence interval and p-value from the comparisons of the optimal recAP dose versus Placebo will be presented.

Discharge from ICU/Intermediate care data will be listed.

Discharge from Hospital for Day 1 to Day 28 and Day 1 to Day 90

Total time in hospital and Time to being discharged from hospital will be analyzed in an identical fashion to the method described above, except the stratified log-rank test will not be performed. Patients that have transferred to another hospital will not be classed as discharged from the hospital. For the calculation of Total time in hospital for Day 1 to 28, if a subject discontinued or died prior to Day 28 whilst still in hospital, the hospital discharge date is assumed as Day 28. For the calculation of Total time in hospital for Day 1 to 90, if a subject discontinued or died whilst still in hospital, then the discharge date will be assumed as taking the maximum of Day 28 or study discontinuation date.

Iohexol substudy

Para-aminohippuric (PAH) will not be included in any analyses or data listings because this product is no longer manufactured.

A single intravenous bolus injection of 5 mL iohexol (Omnipaque 240 mg/mL) will be administered over 5 minutes on Day 1 and on Day 7 or discharge from the ICU, whichever comes first. The bolus will be administered at the start of the 6 ± 1 hour urine collection interval. For the measurement of iohexol, 2 mL blood samples will be collected in EDTA anticoagulated Vacutainer® tubes at the following time points: prior to iohexol bolus administration and at 60, 120, and 360 minutes.

$CL_{Iohexol}$ will be calculated using the concentration values from all time points according to a two-compartment or one-compartment model using the formula:

$CL_{Iohexol} = \text{Dose}/\text{AUC}$ (with AUC: area under the plasma concentration–time curve).

Then, in the case of a one compartment model, plasma clearance of iohexol will be modified for the early distribution phase by the Bröchner–Mortensen (BM) formula:

$CL_{Iohexol} \text{ BM} = (0.990778 \times CL_{Iohexol}) - (0.001218 \times CL_{Iohexol}^2)$ ([Gaspari et al, 1995](#)).

Iohexol plasma concentrations will be listed and summarized using descriptive statistics by timepoints. Iohexol PK parameters will be listed and summarized using descriptive statistics. These summaries will include the number of patients (n), mean, standard deviation (SD), coefficient of variation (CV), minimum, median, maximum, geometric mean, and geometric %CV, when applicable.

Iohexol clearance ($CL_{Iohexol}$), as a gold standard measure of GFR, will be correlated to creatinine clearance in a subset of patients using scatter plots.

Exogenous Creatinine Clearance

To evaluate if renal replacement therapy (RRT) has an effect on endogenous creatinine clearance, the exogenous creatinine clearance by RRT equipment will be assessed by measuring the creatinine concentration in the effluent and effluent volume during the 6 ± 1 hour urine collection interval. This will be only done by the sites participating in the Iohexol substudy.

Standardized exogenous creatinine clearance (mL/min) by the RRT equipment will be calculated by PPD Biostatistics using the following formula.

$$\frac{\text{Effluent Creatinine (mg/dL)}}{\text{Serum Creatinine (mg/dL)}} \times \frac{\text{Total effluent volume collected (mL)}}{\text{Stop date/time – Start date/time of effluent collection (min)}}$$

- The effluent creatinine (mg/dL) will be assessed by the laboratory conducting the Iohexol data.
- The serum creatinine (mg/dL) assessed by the central laboratory and used in the primary endpoint of endogenous creatinine clearance will be used to determine the standardized exogenous creatinine clearance.
- Per protocol, two blood samples are collected to evaluate the serum creatinine, one at the beginning of the urine sample collection and the other at the end of the urine sample collection. The average of these two serum creatinine measurements will be used in the formula above to assess the standardized exogenous creatinine clearance. In case there is only one serum creatinine sample available, then the serum creatinine concentration from that one sample will be used in the formula.
- The number of minutes from the start date/time to the stop date/time of effluent sample collection and the total effluent volume (mL) from the RRT equipment will be derived from data collected at site.

The time-corrected exogenous creatinine clearance will be listed for subjects who are on RRT in the Iohexol population.

A time-course plot of exogenous creatinine clearance on each day will be presented for each subject on RRT in the Iohexol population.

9. Safety Analysis

Safety will be assessed by evaluation of the following variables:

- Adverse events (AE)
- Local Laboratory (Hematology, Clinical Chemistry and Urinalysis parameters not considered in the efficacy analyses)
- Vital Signs
- Physical Examination findings including ECGs

All analyses of safety will be conducted using the Safety Set and will be presented for all 4 treatment groups, for both parts of the study.

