### **6.3.8.7 Glomerular Filtration Rate**

A limited number of sites only will simultaneously determine GFR with iohexol administration and blood sampling (considered the golden standard) to globally compare and assess correlation of GFR and calculated endogenous creatinine clearance. In addition, at these sites samples from the effluent from patients on RRT will be taken to assess exogenous (machine) creatinine clearance. Detailed instructions to these sites for iohexol and exogenous creatinine clearance are provided in Section 13.5.

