## **6.3.9 Renal Replacement Therapy**

From Day 1 to Day 7 only continuous modalities of RRT are allowed. From Day 8 onward, intermittent/non-continuous modalities such as intermittent hemodialysis are allowed.

Initiation of RRT: Initiation of RRT should be based on the criteria described by Bellomo et al (2012).

Meeting at least one criterion of the below makes the patient eligible for initiation of RRT:

1. Anuria (negligible urine output for 6 hours)
2. Severe oliguria (urine output < 200 mL over 12 hours)
3. Hyperkalemia (potassium concentrations > 6.5 mmol/L)
4. Severe metabolic acidosis (pH < 7.2 despite normal or low partial pressure of carbon dioxide in arterial blood)

5. Volume overload (especially pulmonary edema unresponsive to diuretics)
6. Pronounced azotemia (urea concentrations > 30 mmol/L or creatinine concentrations > 300  $\mu$ mol/L)
7. Clinical complications of uremia (e.g., encephalopathy, pericarditis, neuropathy)

Timing of Stopping RRT: Termination of dialysis is based on criteria as used in the VA/NIH Acute Renal Failure Trial Network Study (VA/NIH Acute Renal Failure Trial Network, 2008). If (on continuous renal replacement therapy or between intermittent hemodialysis sessions) diuresis > 30 mL/hour and there are no other indications for RRT, then endogenous creatinine clearance should be calculated using a 6-hour urine collection period. If endogenous creatinine clearance  $\geq$  20 mL/min, RRT should be discontinued. If endogenous creatinine clearance  $\leq$  12 mL/min, RRT should be continued. If endogenous creatinine clearance > 12 mL/min and < 20 mL/min, continuation or termination will be the decision of the treating physician. Exact criterion or criteria, corresponding values (e.g., sodium, potassium, or pH) and deviations (e.g., RRT not started when indicated or RRT started when not indicated) need to be meticulously recorded in the eCRF.

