### **13.5.3 Iohexol Sampling**

For the measurement of iohexol, 2-mL blood samples will be collected in EDTA anticoagulated Vacutainer® tubes at the following time points: prior to iohexol bolus administration and at 60, 120, and 360 minutes. After centrifugation ( $500 \times g$ , 10 minutes), the remaining approximately 1 mL of plasma will be divided into 2 Micronic 1.4-mL cryotubes and stored at  $-80^{\circ}\text{C}$ , until batched shipments to the central laboratory are sent and further processing of one of each cryotubes at the Hillcrest Medical Center, United States, can be done.

Five-milliliter urine samples will be collected prior to the bolus infusions, and the urine bag will be emptied. Starting with freshly produced urine, 5-mL samples will be taken at 60, 120, and 360 minutes directly from the Foley catheter. An additional 5-mL sample will be taken from the combined total volume that was collected during the  $6 \pm 1$  hour urine collection interval. The volumes of urine produced at the 60-, 120-, and 360-minute time points will be entered in the electronic case report form (eCRF). The total volume of urine collected in the  $6 \pm 1$  hour interval will be corrected for the volume of samples taken during this interval and also entered in the eCRF. Urine tubes will be stored at  $-80^{\circ}\text{C}$ , until batched shipments to the central laboratory are sent and further processing of the urine at the Hillcrest Medical Center can be done.

The sample time points of effluent will be at  $t = 360$  minutes of the urine collection interval, analogous to the time points for serum creatinine determinations, as needed for endogenous creatinine clearance calculations. Two samples of 1 mL will be taken from the effluent and stored in Micronic 1.4-mL cryotubes at  $-80^{\circ}\text{C}$ , until batched shipments to the central

laboratory are sent and further processing of one of each cryotube at the Hillcrest Medical Center can be done. The total volume of effluent will be recorded in the eCRF.

Although urine collection for 6 hours is preferred, a time window of  $\pm 1$  hour is allowed for pragmatic reasons adding flexibility to the schedule. In case the urine sampling interval is not exactly 6 hours, the last urine and blood sampling time points will have to match, e.g., with a 5-hour urine collection interval the last urine and blood sample will be obtained at  $t = 300$  minutes.

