### **13.5.5 Statistical Data Analyses**

#### **13.5.5.1 Iohexol and Creatinine Clearance**

Results from the measurement of iohexol and endogenous and exogenous creatinine clearance will be investigated in an exploratory manner with more details provided in the statistical analysis plan (SAP) (e.g., measured GFR, endogenous creatinine clearance in relation to exogenous creatinine clearance).

Iohexol clearance ( $Cl_{\text{Iohexol}}$ ), as a gold standard measure of GFR, will be correlated to creatinine clearance at the different time points in a subset of patients.

The  $Cl_{\text{Iohexol}}$  will be calculated by a 2-compartment model where  $Cl_{\text{Iohexol}} = \text{dose}/\text{area}$  under the curve from 0 to infinity, with extrapolation from 6 hours to infinity, and potentially a more refined model.

Only descriptive methods will be applied for assessing exogenous creatinine clearance.

Effective renal plasma flow will be correlated with the iohexol clearances and creatinine clearances.

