4.3.6. Iohexol

The Iohexol Set includes all patients who were administered iohexol.

5. Patient Disposition

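### In iohexol windows that overlap continuous RRT, Dose/AUC includes machine clearance, so the substudy's reference GFR is biased upward for those points

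*SAP*

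**What the plan says.** **Purpose.** Protocol 6.3.8.7 has a limited number of sites measure GFR with iohexol "to globally compare and assess correlation of GFR and calculated endogenous creatinine clearance". Daily endogenous creatinine clearance is the building block of AUC1-7.

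**Reference method.** In SAP 8.3, iohexol clearance "will be calculated using the concentration values from all time points according to a two-compartment or one-compartment model using the formula" dose over plasma AUC, with a Bröchner-Mortensen adjustment if one compartment is used. Protocol 13.5.5.1 gives the same ratio, with AUC from zero to infinity, "with extrapolation from 6 hours to infinity, and potentially a more refined model". That refined model is not defined. The result, "as a gold standard measure of GFR, will be correlated to creatinine clearance in a subset of patients using scatter plots". The subset is not defined either.

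**Who is included.** SAP 4.3.6: "The Iohexol Set includes all patients who were administered iohexol". Patients on RRT are expected among them, because SAP 8.3 plans a listing and daily plots of exogenous creatinine clearance for those in the Iohexol population who are on RRT.

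**RRT in the same period.** The boluses are given on Day 1 and on Day 7, or at ICU discharge if that is earlier (Protocol 13.5.2). Protocol 6.3.9: "From Day 1 to Day 7 only continuous modalities of RRT are allowed".

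**Where machine clearance is handled.** Protocol 6.3.8.7: "samples from the effluent from patients on RRT will be taken to assess exogenous (machine) creatinine clearance". Protocol 13.5.3 adds: "Two samples of 1 mL will be taken from the effluent", and Table 13-3 schedules this on both iohexol days. The stated use is creatinine only. Neither document describes an effluent iohexol assay.

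**The concern.** The two axes of the scatter plot should estimate the same quantity, native kidney clearance. Creatinine clearance in SAP 8.1 is urine creatinine over serum creatinine, times urine flow, so it counts only what the kidney excretes. Iohexol clearance is inferred from how fast the marker leaves plasma, so anything a filter removes is credited to the kidney. The plan recognises machine removal for creatinine but carries no equivalent into the iohexol calculation.

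The Bröchner-Mortensen step does not help, because it adjusts for the early distribution phase and not for a second elimination route.

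What is at stake is the reading of the substudy. Protocol 13.5.1 itself says that creatinine clearance is not fully representative in unstable conditions such as AKI, and the iohexol data are the trial's only direct comparison with a reference GFR. The distortion falls on patients sick enough to be on RRT, and it always runs in the same direction.

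**Working it through.** The documents state no sample size, agreement limit or expected correlation for this comparison, so there is no planned figure to reproduce.

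**Inputs from the documents**
- Dose: 5 mL × 240 mg/mL = 1200 mg (Protocol 13.5.2).
- Native clearance scale on RRT: discontinue at 20 mL/min or more, continue at 12 or less, physician's choice between (Protocol 6.3.9).
- Assumed placebo mean AUC1-7: 60 mL/min (SAP 4.1).

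**Assumption, not in the documents:** machine clearance of iohexol of 15, 25 or 40 mL/min.

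**Step 1, mass balance.** With linear elimination, Dose/AUC(0 to infinity) = native + machine clearance. The ratio to native clearance is therefore (native + machine)/native. For example, (20 + 15)/20 = 1.75 and (12 + 40)/12 = 4.33.

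| Native (mL/min) | Machine 15 | Machine 25 | Machine 40 |
|---|---|---|---|
| 12 | 27 (2.25×) | 37 (3.08×) | 52 (4.33×) |
| 20 | 35 (1.75×) | 45 (2.25×) | 60 (3.00×) |
| 40 | 55 (1.37×) | 65 (1.62×) | 80 (2.00×) |
| 60 | 75 (1.25×) | 85 (1.42×) | 100 (1.67×) |

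A two-compartment model (assumed volumes 8 L and 10 L, intercompartmental flow 100 mL/min) returns the same values. With machine clearance set to zero it returns the native value. At native 20 and machine 40, the reading of 60 mL/min equals the assumed placebo mean.

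**Step 2, SAP adjustment.** CL(BM) = 0.990778 × CL − 0.001218 × CL². For CL = 35: 34.68 − 1.49 = 33.2. At native 20 the adjusted readings are 33.2, 42.1 and 55.1. At native 12 they are 25.9, 35.0 and 48.2. The excess remains.

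**Step 3, effect on the plot.** Illustrative simulation, 4000 repeats of 30 points. Assumed: native clearance uniform 0 to 20 on RRT; mean 60, SD 30, floor 12 off RRT; machine clearance uniform 15 to 40; log-scale error SD 0.15 for creatinine and 0.10 for iohexol.

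| On RRT | Mean iohexol − creatinine, as planned | Machine term removed | r as planned | r, machine term removed |
|---|---|---|---|---|
| 0% | −0.4 | −0.4 | 0.92 | 0.92 |
| 10% | +2.4 | −0.4 | 0.90 | 0.94 |
| 20% | +5.1 | −0.4 | 0.89 | 0.95 |
| 30% | +8.0 | −0.3 | 0.88 | 0.96 |
| 40% | +10.8 | −0.2 | 0.87 | 0.96 |

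Differences are in mL/min. The 0% row shows what a plot restricted to off-RRT windows would look like under these assumptions. The documents give no RRT share, so the rows show sensitivity and are not forecasts.

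**Step 4, when overlap can occur.** Exclusion criterion 6 removes patients already on RRT or with a decision to start it within 24 hours of planned dosing, so overlap at the Day 1 bolus should be rare. Patients leaving the ICU before Day 7 get the second bolus at discharge, when continuous RRT is unlikely. What remains is chiefly patients in the ICU and on RRT at Day 7.

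**The case against.** Four points can be made for leaving the plan as it is.

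- **It is exploratory.** The output is scatter plots and descriptive summaries at a few sites, with no test, calibration or decision rule. The primary ANOVA and combination test do not use iohexol. This stands. A reader might infer that the primary result is biased, or that the plan lets the substudy overturn the endpoint. The documents support neither.
- **Exposure is narrow.** A reader might infer that both boluses are contaminated. Exclusion criterion 6 and the dosing rule at ICU discharge make that unlikely, as Step 4 shows. This stands.
- **Affected patients can be found.** RRT dates and times are collected, RRT data are listed, and machine creatinine clearance is plotted for each such patient. That allows a careful reader to spot the problem, but the planned plot would still present those points as reference GFR. The undefined refined model and the undefined subset could have been the place for a rule, but none is written.
- **The size is uncertain.** A reader might take a fixed minimum inflation, such as a doubling, from the RRT stopping threshold. The documents do not support one. The ratio is 1.75 at machine clearance 15 and native 20. Stopping also requires diuresis above 30 mL/hour and no other indication, and clinical judgement may override the criteria, so some patients on RRT may have native clearance above 20 and a smaller ratio.

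The objection limits reach and size. It does not answer the mismatch between the axes.

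**Conclusion.** The point holds within limits. For iohexol windows overlapping continuous RRT, the planned formula gives native plus machine clearance and labels it GFR. The direction is upward and follows from the formula, provided that the filter removes any iohexol at all. The size rests on an assumed machine clearance: about 1.8 to 3.0 times native at 20 mL/min and 2.3 to 4.3 times at 12 mL/min over 15 to 40 mL/min, shrinking as native clearance rises. Points off RRT and the primary analysis are unaffected. How far the overall plot shifts depends on the share of on-RRT windows, which the documents do not give. This is a wrong rule for a minority of points in a supporting analysis, and it is worth correcting because those points would be read as creatinine clearance failing in the sickest patients.

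**What to change.** In SAP 8.3 and Protocol 13.5.5.1:

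- State that Dose/AUC is not used as GFR for an iohexol window that overlaps RRT, taking the window from the bolus to the last blood sample. RRT start and stop dates and times are already in the eCRF (Protocol 6.3.9). Temporary stops need not be recorded, so classify a window by recorded RRT status without trying to adjust for short interruptions.
- Define the subset for the main scatter plot as windows off RRT. Show on-RRT windows separately with a distinct symbol, labelled as total (native plus machine) clearance.
- Urinary iohexol clearance from the timed urine already collected may be added for on-RRT windows as a supplementary display only. It shares urine volume and collection-time error with creatinine clearance, so part of any agreement is built in. To illustrate, assume log-scale SDs of 0.5 for native clearance, 0.2 for volume error and 0.1 for each assay. The correlation is then (0.25 + 0.04)/0.30 = 0.97 with urinary iohexol, against 0.25/√(0.30 × 0.26) = 0.90 with an independent reference. In anuria both values are zero and the comparison is uninformative.

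The cost is a few sentences and minor programming, with a few fewer points in the main plot. No treatment, visit or sample changes.
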